4.3 Data safety monitoring board

The Data and Safety Monitoring Board (DSMB) will monitor participant safety, data quality and evaluate the progress of the study. The constitution, activities and reports of the DSMB shall be governed by the FDA's "Guidance for Clinical Study Sponsors: Establishment and Operation of Clinical Study Data Monitoring Committees" (detailed in a study specific DSMB charter). Both documents will be distributed to all DSMB members.

The DSMB will be an external group of experts, independent of the sponsor and consist of at least three physicians of which one will be the DSMB chairman.

5 Patient selection criteria

5.1 Screening

To be eligible for the study patients have to meet all inclusion criteria and no exclusion criteria. If the patient has been screened and meets all inclusion and no exclusion criteria and does not receive the dose within 28 days, for reasons such as the patient did not receive an organ offer within the time frame etc., the patient may be rescreened. No other rescreening is allowed. The re-screening procedure will be the same as the previous screening visit with the exception for the virology tests which do not have to be repeated if not more than 6 months old. Medical history and concomitant medication will be updated if applicable. Re-screened patients will keep the original screening number.

5.2 Inclusion criteria

1. Male or female age 18-70 years at the time of screening
2. Patients on the kidney transplant waitlist who have previously undergone desensitization unsuccessfully or in whom effective desensitization will be highly unlikely. The breadth and strength of sensitization will predict an extremely low likelihood of successful desensitization or kidney paired donation.
3. Patients with a live or deceased donor with a positive crossmatch test.
4. Patient must be able to understand and sign the informed consent.

5.3 Exclusion criteria

1. Previous treatment with IdeS
2. Previous high dose IVIg treatment (2 g/kg BW) within 28 days prior to IdeS treatment.
3. Lactating or pregnant females
4. Women of child-bearing age who are not willing or able to practice FDA-approved forms of contraception.
5. HIV-positive patients
6. Patients with clinical signs of HBV or HCV infection
7. Patients with active tuberculosis
8. A significantly abnormal general serum screening lab result according to the investigator's judgement. Hgb cannot be < 6.0 g/dL. Laboratory safety results from within 3 days before screening can be used
9. Severe other conditions requiring treatment and close monitoring, e.g. cardiac failure \geq NYHA (New York Heart Association) grade 3, unstable coronary disease or oxygen dependent COPD
10. Individuals deemed unable to comply with the protocol
11. Patients with clinical signs of CMV or EBV infection
12. Patients with a history of major thrombotic events, patients with active peripheral vascular disease or patients with proven hypercoagulable conditions
13. Patients should not have received investigational drugs within 4 half-lives (or similar)

14. Known allergy/sensitivity to IdeS infusions
15. Patients who have a live donor and test positive for ImmunoCAP anti-IdeS IgE

5.4 Withdrawal criteria

5.4.1 Criteria for discontinuation from the study

Patients may be discontinued from study treatment and assessments at any time. The patient is free to discontinue his/her participation in the study at any time and for any reason, without prejudice to further treatment. If a patient is withdrawn from the study by the investigator due to adverse events he/she will not be replaced. Patients who withdraw for reasons other than adverse events may be replaced.

The study may be stopped prematurely if:

1. DSMB recommend that the study should be terminated
2. Findings that, at the discretion of Principal Investigator(s) and/or Sponsor, indicate that further dosing should be stopped

5.4.2 Procedures for discontinuation of a patient from the study

A patient who discontinues after study drug administration will always be asked about the reason(s) for discontinuation and the presence of any adverse events. If possible, he/she will be seen and assessed by an investigator(s). Adverse events will be followed. If possible, patients who discontinue from the study before completion should undergo the assessments and procedures scheduled for the end of study follow up visit. Patients who, for a medical reason, cannot comply with the protocol procedures will be followed by best procedure to retrieve safety and efficacy data.

If the study is prematurely terminated, the Sponsor will promptly inform the investigators and the regulatory authorities of the termination and the reason(s) for the termination. The IRBs/IECs will also be promptly informed and provided the reason(s) for the termination either by Sponsor or investigators, depending on local requirements. All patients, those in the study at the time for termination as well as those that have completed the study, will be informed about the study termination and the reason(s) for it by their respective investigator.

6 Study conduct

6.1 Study treatment

6.1.1 IdeS

IdeS is a clear colorless liquid. It is formulated at 10 g/L in PBS and intended for intravenous administration after dilution. Refer to [Table 4](#) for composition.

[REDACTED]

[REDACTED]	[REDACTED]	[REDACTED]
[REDACTED]	[REDACTED]	[REDACTED]
[REDACTED]	[REDACTED]	[REDACTED]
[REDACTED]	[REDACTED]	[REDACTED]
[REDACTED]	[REDACTED]	[REDACTED]
[REDACTED]	[REDACTED]	[REDACTED]
[REDACTED]	[REDACTED]	[REDACTED]

6.1.2 Storage and handling

All patients will receive treatment with IdeS. IdeS will be supplied to the hospital pharmacy [REDACTED] in 15 mL vials, each containing 7 mL IdeS packed into cartons containing 10 vials each. Vials should be kept dark at - 20°C. IdeS infusion solution will be prepared at the study unit. Administration will be performed using an infusion syringe or infusion bag with a filter containing infusion set and an infusion pump. Details on preparation, labeling and administration of IdeS are described in the pharmacy manual.

6.1.3 Drug accountability and compliance check

The administration of all medication (including investigational products) must be recorded in the appropriate sections of the CRF. Treatment compliance will be assured by supervised administration of the investigational product by the investigator or delegate. The dose, date and time of administration of the investigational product will be checked by the monitor at monitoring visits.

It is the principal investigators/institution's responsibility to establish a system for handling study treatments, including investigational medicinal products, to ensure that:

1. Deliveries are correctly received by a responsible person (e.g. pharmacist or designated study personnel)
2. Deliveries are recorded
3. Study treatments are handled and stored safely and properly
4. The study drug provided for this study will be used only as directed in the study protocol
5. The study personnel will account for all drugs dispensed and returned. Any discrepancies must be documented, investigated and appropriately resolved
6. At the end of the study, the pharmacy personnel will account for all unused drugs and for appropriate destruction/return of all unused drugs to the sponsor for destruction. Certificates of delivery, destruction and return must be signed by a study team member

6.1.4 Administration of investigational drug

Intravenous IdeS will be administered over at least 15 minutes. The first 3 patients will receive one dose of 0.25 mg/kg BW IdeS on study day 0. If it is considered safe and the desired effect is not achieved (negative crossmatch test) after the first dose, an additional IdeS infusion can be given within 2 days of the first infusion. The dose schedule may be increased to 0.5 mg/kg BW given once or twice after the first 3 patients have been tested. The decision to escalate the dose will be done after evaluation of safety and efficacy as described in section 4.2.

6.1.5 Desensitization protocol

In addition to treatment with IdeS, patients will be treated with high dose IVIg 10% solution 2 g/kg BW (max 140g for >70kg) 7 days after IdeS treatment and 1 g rituximab (anti-CD20) 9 (-11) days after IdeS treatment. If deemed necessary by the investigator the IVIg dose may be split into two doses administered over days 6-8.

6.1.6 Premedication

Patients will receive premedication with glucocorticoids (methylprednisolone, 250 mg intravenously) and antihistamines (loratadine 10 mg orally or an equipotent antihistamine) before each IdeS infusion.

6.1.7 Prophylactic antibiotic

All patients will receive prophylactic antibiotics or sulpha according to clinical practice at each site from the start of IdeS treatment until serum IgG level is back within normal range.

6.1.8 Induction therapy

Induction therapy can be used if indicated. Sites are allowed to use either ATGAM (anti thymocyte globuline derived from horse) or Alemtuzumab (anti-CD52 antibody). Rabbit ATG cannot be used since it is efficiently cleaved by IdeS. Alemtuzumab can be given 4 days after IdeS at the earliest, based on limited experience. If alemtuzumab is used as induction therapy on day 4, pulse steroid treatment can be used up to day 4 to prevent T-cell mediated rejection.

6.1.9 Immunosuppressing agents

Patients will be treated with immunosuppressing agents according to clinical practice at each study center.

6.1.10 Other concomitant medication

Supportive therapy considered necessary for the patient's welfare may be given at the discretion of the investigator. All concomitant medication, including premedication and prophylactic antibiotics must be recorded on the concomitant medication page in the CRF.

6.2 Study procedures described per visit

Visit 1 (Screening day -28 to day 0)

At the screening visit each subject will be informed about the study and after signing the informed consent form assessments for eligibility will commence. Eligibility evaluation, collection of concomitant medication, demographic data (age, sex, race, height, weight and BMI) and medical and surgical history is performed. A full physical examination, height and weight measurements, vital signs including resting blood pressure, pulse, respiratory

frequency, 12-lead resting ECG and body temperature is done. Additionally blood sampling for serology (HIV, hepatitis, BK, EBV and CMV), pregnancy test and clinical chemistry, hematology as well as blood samples for analysis of DSAs, CDC- and FACS-CXM and anti-IdeS IgE antibody analysis (ImmunoCAP) will be collected.

Visit 2 (days 0-2)

Patients found eligible at the screening visit will be included in the study. At visit 2 the eligibility check will be repeated within 60 min from IdeS dosing. A pregnancy test will be taken. If a female patient has been hospitalized between screening visit and visit 2, a pregnancy test at screening visit will suffice and a pregnancy test at visit 2 is not required. In addition methylprednisolone and loratadine will be administered predose to prevent infusion reactions. Vital signs, body temperature, safety laboratory sampling, pharmacokinetic and pharmacodynamics sampling will be performed pre-dose, 2 h, 6 h, 24 h and 48 h post IdeS infusion. In addition blood sampling for DSAs will be drawn at pre-dose, 2 h, 6 h, 24 and 48 h. Blood sampling for CDC- and FACS-CXM will be done at pre-dose, 2 h, 6 h, and 24 h. Any effort should be made to obtain crossmatch test for all time-points indicated in the study flowcharts. If this is not possible due to logistics on specific sites, the sponsor can allow a smaller number of time-points to be evaluated. However, as a minimum one crossmatch test pre-dose and one post-dose IdeS must be performed to allow evaluation of the primary endpoint. ADA will be sampled at pre-dose and 48 h post IdeS infusion. P-creatinine will be measured at 24 h and 48 h post IdeS infusion and eGFR will be calculated. Repeat 24 hour urine collections will be performed day 1-9 for urine protein electrophoresis analysis. AEs and concomitant medication will be recorded in the CRF throughout the visit. AEs that occur in the time period prior to administration of the study drug should be recorded as part of the patient's medical history but will not be considered a treatment emergent adverse event (TEAE) unless directly related to study procedures (e.g. hematoma secondary to laboratory testing) or it meets the definition of an SAE. A kidney biopsy on the donor kidney will be performed in deceased donor patients.

Visit 3 (day 3-6)

Twenty-four- (24)-hour urine collections will be performed daily, day 1-9, for urine protein electrophoresis analysis. AE and concomitant medication will be assessed. PK will be drawn at 96 hours \pm 4h.

Visit 4 (day 7)

At visit 4 high dose IVIg (2 g/kg BW) will be administered. Prior to IVIg dosing the following assessments are made: vital signs, blood sampling for analysis DSAs, safety laboratory parameters, PK, PD, ADA and P-creatinine. The eGFR will be calculated. Additional samples for PD and ADA will be drawn after the IVIg infusion. If the IVIg dose is split into two doses given over two days the sampling will be performed before and after the first dosing. Repeat 24 hour urine collections will be performed day 1-9 for urine protein electrophoresis analysis. AE and concomitant medication will be assessed.

Visit 5 (Day 9)

At visit 5 the patient will be dosed with rituximab. In addition a blood sample for PK and PD analysis will be drawn. Repeat 24 hour urine collections will be performed day 1-9 for urine protein electrophoresis analysis. AE and concomitant medication will be assessed.

Visit 6 (day 14)

At visit 6 the patient will be assessed for body weight, AEs and concomitant medication. Blood sampling for analysis of DSAs, safety laboratory tests, P-creatinine/eGFR, PK, PD, ADA and virus screen for BK, EBV and CMV will be drawn. Urine will be obtained for analysis of proteinuria.

Visit 7 (day 21)

Blood sampling for assessment of DSAs, safety laboratory parameters, PD, ADA and P-creatinine/eGFR will be drawn. In addition AEs and concomitant medication will be assessed. **Visits 8 and 9 (day 28 and 64)**

At visits 8 and 9 the patient will be assessed for AEs and concomitant medication. Blood sampling for analysis of DSAs, safety laboratory tests, PD, ADA, P-creatinine/eGFR and virus screen for BK, EBV and CMV. Urine will be obtained for assessment of proteinuria. At visit 8 vital signs will also be assessed.

Visits 10 and 11 (day 90 and 120)

At visits 10 and 11 the patient will be assessed for vital signs, AEs and concomitant medication. Blood sampling for analysis of DSAs, safety laboratory tests, ADA and P-creatinine/eGFR. At visit 9 a blood sample for virus screen (BK, EBV and CMV) will also be drawn. Urine will be obtained for assessment of proteinuria.

Visit 12 (day 180, end of study)

A follow-up visit will be performed 180 +/- 14 days following IdeS infusion. This will be considered the end of study for the patient. At this visit the patient will be assessed for vital signs, ECG, AEs and concomitant medication. Blood sampling for analysis of DSAs, pregnancy test, safety laboratory tests, P-creatinine/eGFR, PD and ADA will be performed and e GFR calculated. Urine will be obtained for assessment of proteinuria and a physical examination will be performed. A kidney biopsy will be performed to assess kidney status.

6.3 Safety reporting

It is of the utmost importance that all staff involved in the study is familiar with the content of this section. The principal investigator is responsible for ensuring this.

6.3.1 Definition of adverse events

An adverse event (AE) is the development of an undesirable medical condition or the deterioration of a pre-existing medical condition following or during exposure to a pharmaceutical product, whether or not considered causally related to the product. Relationship to the study drug will be deemed as not related, unlikely, possible or probable. An undesirable medical condition can be symptoms (e.g. nausea and chest pain), signs (e.g. tachycardia and enlarged liver) or the abnormal results of an investigation (e.g. laboratory findings and electrocardiograms).

In cases of surgical or diagnostic procedures, the condition/illness leading to such a procedure is considered as the AE rather than the procedure itself.

In case of fatality, the cause of death is considered as the AE, and the death is considered as its outcome.

Pre-treatment adverse event:

A pre-treatment adverse event is any untoward medical occurrence arising or observed between signing of informed consent and the first administration of the IMP.

Treatment emergent adverse event:

A treatment emergent adverse event is any AE occurring after the administration of the IMP and within the time of the follow up period or a pre-treatment adverse event or pre-existing medical condition that worsens in intensity after administration of the IMP and within the time of the follow up period.

6.3.2 Definitions of serious adverse event

A serious adverse event (SAE) is an AE or suspected adverse reaction (SAR) that is considered “serious” if, in the view of either the investigator or sponsor, it results in any of the following outcomes:

- Results in death
- Is immediately life-threatening
- Requires in-patient hospitalization or prolongation of existing hospitalization. Regular dialysis treatment in or outside hospital is not included
- Hospitalization for transplantation is not considered an SAE
- Results in persistent or significant disability or incapacity
- Is a congenital abnormality or birth defect
- Is an important medical event that may jeopardize the patient or may require medical intervention to prevent one of the outcomes listed above

Life-threatening event: An adverse event or suspected adverse reaction is considered “life-threatening” if, in the view of either the investigator or sponsor, its occurrence places the patient or subject at immediate risk of death. It does not include an adverse event or suspected adverse reaction that, had it occurred in a more severe form, might have caused death.

Disability is defined as a substantial disruption in a person’s ability to conduct normal life functions.

Hospitalization for inpatient hospitalization or prolongation of existing hospitalization. In this study the following will not qualify as an SAE. Elective treatment of a pre-existing condition that did not worsen during the clinical investigation is not considered an AE. Hospitalization for study drug dosing and observation as required by protocol is not considered an SAE. Admittance to an emergency room for observation without being

admitted to the hospital may be considered to be an AE but is not considered as an SAE. However, complications that occur during hospitalization are AEs, and if a complication prolongs hospitalization, the event is considered serious. Regular dialysis treatment in or outside hospital is not considered an AE or SAE.

Important medical events that may not result in death, be life-threatening, or require hospitalization may be considered serious when, based upon appropriate medical judgment, they may jeopardize the patient or subject and may require medical or surgical intervention to prevent one of the outcomes listed in this definition. Examples of such medical events include allergic bronchospasm requiring intensive treatment in an emergency room or at home, blood dyskrasias or convulsions that do not result in inpatient hospitalization, or the development of drug dependency or drug abuse.

SAEs should be followed until the event resolves, stabilizes, or returns to baseline. If the patient is discontinued from the study prior to resolution/stabilization of the SAE, then the patient will be followed as part of the SAE/pharmacovigilance system.

6.3.3 Recording of adverse events

In clinical studies, an AE/SAE can occur at any time after signing of the informed consent until the end of the study, including run-in or washout periods, even if no study treatment has been administered, e.g. and AE can be related to a procedure in the protocol.

AEs will therefore be collected on the AE CRF from the time of signing of the informed consent and throughout the study period including the follow-up period. However, AEs that occur in the time period between informed consent and administration of the trial drug should be recorded as part of the patient's medical history, but will not be considered a treatment emergent adverse event (TEAE) unless directly related to study procedures (e.g. hematoma secondary to laboratory testing) or it meets the definition of an SAE.

6.3.4 Variables

The following variables will be recorded in the CRF for each AE; description of the AE, the date and time (if applicable) when the AE started and stopped, intensity according to Common Toxicity Criteria grade (CTCAE v.4.03), seriousness of the AE, causality rating, action taken with regard to investigational product, if AE caused patient to discontinue the study and outcome.

For each reported AE the investigator will assess a causal assessment of the relationship of the event to study procedures and/or IdeS using the following criteria.

- **Unrelated;** applicable to an AE that occurs when the subject was not exposed to study treatment or another cause is obvious:
 - The AE does not meet the above criteria
 - There is sufficient information that the etiology of the AE is not related to the study drug
- **Unlikely to be related:** applicable to an AE that meets the following criteria:
 - Does not follow a reasonable temporal sequence from dosing of IdeS

- May readily have been produced by the patient's clinical state, environmental, or toxic factors, or other therapy administered to the patient
- **Possibly related:** applicable to AEs where connection with IdeS dosing appears unlikely but cannot be ruled out. Applicable to AEs where:
 - It follows a reasonable temporal sequence following dosing of IdeS
 - It follows a known pattern of response to dosing of IdeS (based on animal studies)
- **Probably related:** applicable to AEs that are considered, with a high degree of certainty, to be related to IdeS. Applicable to AEs where:
 - It follows a reasonable temporal sequence from dosing of IdeS
 - It cannot be reasonably explained by the known characteristics of the patient's clinical state, environmental or toxic factors, or other modes of therapy
 - It follow a known pattern of response to IdeS (based on animal data)

For SAEs, causal relationship will also be assessed for any study procedure.

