#### **Summary tables will be prepared for:**

- All TEAEs
- TEAEs by causality (related/unrelated)
- TEAEs by intensity
- Related TEAEs by intensity
- SAEs
- SAEs by causality (related/unrelated)

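### The related/unrelated AE tables cover one 30-day window with no split at IVIg, and the protocol names two different objects for the causality rating

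*Protocol*

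**What the plan says.** **Object of the rating.** Protocol 6.3.1: "Relationship to the study drug will be deemed as not related, unlikely, possible or probable". Protocol 6.3.4, for every event: "For each reported AE the investigator will assess a causal assessment of the relationship of the event to study procedures and/or IdeS". The same section closes with an addition for serious events only: "For SAEs, causal relationship will also be assessed for any study procedure". Neither section has a causality item for IVIg or rituximab.

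**Other infusions.** Protocol 6.1.5: "In addition to treatment with IdeS, patients will be treated with high dose IVIg 10% solution 2 g/kg BW". The infusion is set 7 days after IdeS and may be split over days 6-8. Rituximab follows on day 9, with latitude to day 11.

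**Analysis.** SAP 4.5.1 counts a new event as treatment-emergent if it starts within a residual-effect period of 30 days after administration. Among the planned summaries is "TEAEs by causality (related/unrelated". SAP 4.1 sets the columns of the safety tables as one dose, two doses and total. No summary table by time of onset is described. The SAP does not say which of the protocol's four grades count as related, or related to what. It does plan a listing of TEAEs ordered by patient and start time.

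**The concern.** The trial has one arm, so no control rate shows which events would have occurred without imlifidase. Attribution rests on the investigator's rating and on when the event began. The rating has two different stated objects in the protocol, and the planned summary tables do not use timing.

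This matters most for delayed effects. Protocol 2.5 says that IgG begins to return, and antibodies to IdeS can appear, at about day 7. Protocol 2.6 names infection as a risk of IgG removal and reports signs of serum sickness in two IdeS-treated patients in another study. Delayed immune reactions and infections are therefore imlifidase questions, and the period in which they would appear overlaps with IVIg and rituximab. A reader of the related-TEAE table alone could not tell how many events began before either product was given.

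**Working it through.** The plan states no figure on this point, so there is none to reproduce. The check compares the texts and adds one line of arithmetic.

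**Step 1. What is rated against what.**

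| Place | Events | Rated against |
|---|---|---|
| Protocol 6.3.1 | all AEs | study drug, four grades |
| Protocol 6.3.4, opening | all AEs | procedures and IdeS in one rating |
| Protocol 6.3.4, closing line | SAEs only | any study procedure, in addition |

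For a non-serious event the second row merges two objects that the first row does not merge. The missing IVIg or rituximab item is not confined to non-serious events: the added SAE rating concerns procedures, and the protocol does not say that these infusions are procedures.

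**Step 2. How the four grades in 6.3.4 treat other therapy.**

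- Unrelated: applies, among other cases, when there is another obvious cause.
- Unlikely: includes events of which it can be said "May readily have been produced by the patient's clinical state, environmental, or toxic factors, or other therapy administered to the patient".
- Possibly: "It follows a reasonable temporal sequence following dosing of IdeS", together with a known response pattern. Other therapy is not excluded.
- Probably: "It cannot be reasonably explained by the known characteristics of the patient's clinical state, environmental or toxic factors, or other modes of therapy".

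A recognised IVIg or rituximab reaction is thus steered towards the two lower grades. An event that fits either explanation can sit in *possibly*, and the SAP does not say on which side of its two-way split *possibly* falls.

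**Step 3. Share of the window after each infusion.** Inputs are the 30-day period (SAP 4.5.1) and the infusion day d (Protocol 6.1.5). The assumptions are a single imlifidase dose on day 0 and infusions given as scheduled. Share = (30 − d)/30.

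| Infusion | d | Share of days after it |
|---|---|---|
| IVIg, earliest | 6 | 24/30 = 80% |
| IVIg, nominal | 7 | 23/30 = 77% |
| IVIg, latest | 8 | 22/30 = 73% |
| Rituximab, nominal | 9 | 21/30 = 70% |
| Rituximab, latest | 11 | 19/30 = 63% |

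SAP 4.1 reports three patients with a second dose, and the SAP does not say which dose starts the 30 days. If the second dose is on day 2 and the period runs from it, the span from the first dose is 32 days. The share after IVIg is then 25/32 = 78% with IVIg on day 7, or 23/32 = 72% if IVIg is timed 7 days after the second dose (day 9). The picture hardly changes.

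The window is also only approximately 30 days. Worsening of pre-treatment events or pre-existing conditions counts through follow-up, and any such worsening after day 30 also comes after both infusions where they were given.

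**Step 4. What the data allow.** Protocol 6.3.4 records the start date of each event and, where applicable, the time. Protocol 6.1.3 requires all medication administration to be entered in the CRF. Onset relative to the first IVIg infusion can therefore be derived; the planned summary tables do not use it.

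**The case against.** The strongest reply is that attribution is already built in. The grades refer to IdeS or the study drug, 6.3.1 names the study drug, and three of the four grades bring other causes or other therapy into the judgement. With 15-20 patients, the start-time listing lets a reader pick out events before IVIg by hand. The table shells are kept in separate documents that are not available here. The study is descriptive, and the period before IVIg is not clean either: transplantation, methylprednisolone, an antihistamine, prophylactic antibiotics and ATGAM or day-4 alemtuzumab may all fall within it.

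Most of this stands, and it rules out several stronger readings:

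- A reader might infer that the related tables cannot separate imlifidase reactions from IVIg or rituximab reactions, or that they simply mix three products. The grading criteria contradict this.
- A reader might infer that investigators will split over whether IVIg is a study procedure. No section classes it as one, and the only example given of a procedure-related event is a hematoma from laboratory testing.
- A reader might infer that *probably* is closed off from day 7. The criterion asks whether other therapy reasonably explains the event, not whether another drug was given.

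The reply does not answer two points. The two rating sentences still differ, and a listing does not give counts of patients and events by period. The tables are what will be cited.

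**Conclusion.** The point holds in limited form. Protocol 6.3.1 and 6.3.4 disagree on the object of the causality rating, and the SAP's summary tables pool a window of which about 73-80% of days follow protocol-specified IVIg and 63-70% follow rituximab. Attribution is partly possible from the criteria and the listing, but the tables do not show it.

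The percentages are shares of calendar days under the scheduled infusion days. They are not shares of events or of risk, and it would be wrong to read them as the fraction of related events that is confounded. The documents do not allow that number to be derived. The primary endpoint is unaffected; what suffers is the interpretability of the main safety tables in a single-arm study.

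**What to change.** 1. **SAP 4.5.1, onset split.** Add TEAE and related-TEAE tables split by onset: before, versus from, each patient's actual first IVIg start. If the IVIg dose was divided, use the first part. Patients who never receive IVIg stay in the first period. State how an event on the IVIg day with no recorded time is assigned. Show patients and patient-days at risk per period, because the periods differ in length.
2. **SAP 4.5.1, definition.** State that related means possibly or probably related to imlifidase.
3. **Protocol 6.3.1 and 6.3.4.** Reconcile them so that the rating refers to IdeS alone. Rate study procedures separately for all AEs if collection is still possible. The SAP (version 1.0, July 2018) describes dosing in the past tense, so this may come too late. For the same reason, separate ratings for IVIg and rituximab are not asked for.

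**Cost.** Items 1 and 2 need programming and a few lines of text, using dates already collected. Cells become smaller in a study of 15-20 patients. The split removes two confounders from the first period, not all: surgery, premedication and induction therapy remain. It also cannot attribute individual events that begin after IVIg.
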